#### 7.3.4 Safety Assessments

Planned time points for all safety assessments are provided in Table 4.

#### 7.3.4.1 Adverse Events

All AEs and SAEs will be collected at the time points specified in Table 4 from the time of informed consent completion until study participation is complete. Any preexisting medical conditions or signs/symptoms present in a subject prior to obtaining informed consent are not considered AEs in the study and should be recorded in the Medical History section of the eCRF. See Section 9.2 and 9.3 for further details.

#### 7.3.4.2 Slit Lamp Biomicroscopy

Slit lamp biomicroscopy assessments will be performed using the ISO11980 grading at the Screening/Baseline visit (D1) and at Visit 3 (and at unscheduled and early exit visits, as necessary).

A biomicroscopy examination of the cornea, adnexa and anterior segment of the eye will be performed, OD and OS, at the Screening/Baseline visit (D1) and at Visit 3 (and at unscheduled and early exit visits, as necessary), and recorded on eCRFs. Record both eyes for the same subject if both are noted to have such a finding.

If warranted, a short slit lamp video or slit lamp photograph should be recorded to demonstrate any abnormal findings or findings of interest during biomicroscopy (for example inferior arcuate staining). Record both eyes for the same subject if both are noted to have such a finding.

# Limbal hyperemia

Limbal hyperemia (redness) will be recorded on a 5-point scale as follows:

0 = None	No hyperemia
1 = Trace	Slight limbal hyperemia (mild segmented)
2 = Mild	Mild limbal hyperemia (mild circumcorneal)
3 = Moderate	Significant limbal hyperemia (marked segmented)
4 = Severe	Severe limbal hyperemia (marked circumcorneal)

### Bulbar Hyperemia

Bulbar conjunctival hyperemia (redness) will be recorded on a 5-point scale as follows:

0 = None	No hyperemia
1 = Trace	Slight regional hyperemia
2 = Mild	Diffuse hyperemia
3 = Moderate	Marked regional or diffuse hyperemia
4 = Severe	Diffuse episcleral or scleral hyperemia

#### • Corneal Epithelial Edema

Corneal epithelial edema should be classified according to the number of microcysts observed. The presence/absence of fluid-filled or debris-filled cysts should be documented.

0 = None	No microcysts; normal transparency
1 = Trace	1 to 20 microcysts; barely discernable local epithelial haziness
2 = Mild	21 to 50 microcysts; faint but definite localized or generalized haziness
3 = Moderate	51 to 100 microcysts; significant localized or generalized haziness
4 = Severe	> 100 microcysts; definite widespread epithelial cloudiness giving a dull glass
	appearance to the cornea or numerous coalescing bullae

#### • Corneal Staining

#### Corneal Staining Set Up

All corneal staining observations should be carried out using a blue excitation light to full intensity and magnification at 16x in conjunction with a yellow barrier filter in the observation system (approximate beam width 10 mm and height 8 mm).

Apply one drop of fresh, non-preserved, sterile saline to the tip of a Sodium Fluorescein (NaFl) impregnated strip. Allow saline to drip off the strip (i.e., without a shaking motion).

Ask the subject to look up and nasally. Gently retract the lower lid and touch the strip to the inferior temporal bulbar conjunctiva, approximately 5 mm or more from the limbus, for 1 to 2 seconds, so that 1 to 2 mm of the flat side of the strip makes contact with the ocular surface. Withdraw the strip and release the lower lid.

[figure not shown]
# o Corneal Staining - Standard Assessment

Record grade according to the following scale:

0 = None	No staining		
	Minimal superficial staining or punctate staining		
1 = Trace	a) Dimpling, discrete dot staining, or		
	b) Trace superficial lens insertion marks or foreign body tracks		
2 = Mild	Regional or diffuse punctate staining		
	a) Central or generalized, or		
	b) Peripheral including 3 to 9 o'clock staining, or		
	c) Foreign body tracks		
	Dense coalescent staining up to 2 mm in diameter		
3 = Moderate	a) Corneal abrasion		
	b) Foreign body track		
4 = Severe	Dense coalescent staining greater than 2 mm in diameter		

The location of staining observed should be recorded in source documentation only, as indicated in Figure 3:

Figure 3. Corneal Regions for Recording Location

Recurrent erosion and corneal ulceration should be recorded under "Other findings."

Inferior arcuate staining should be recorded under "Other findings."

## • Conjunctival Staining

Conjunctival staining should be assessed immediately after corneal staining. Therefore, an additional application of NaFl is not required. However, if needed in order to make a sound judgment, one more application can be made following the instructions given in the section above and using a new NaFl strip. All conjunctival staining observations should be carried out using a blue excitation light in conjunction with a yellow barrier filter in the observation system after NaFl instillation.

Conjunctival staining will be assessed on a 5-point scale:

0 = None	No staining
1 = Trace	Minimal regional staining
2 = Mild	Regional or diffuse punctate staining
3 = Moderate	Significant dense coalescent staining
4 = Severe	Severe dense geographical staining

# • Palpebral Conjunctival Observations

The severity of the maximal palpebral conjunctival response will be recorded on a 5-point scale as follows:

0 = None	Uniform satin appearance of the conjunctiva			
1 = Trace	Slight conjunctival injection without texture			
2 = Mild	Mild or scattered papillae/follicles less than 1 mm in diameter			
3 = Moderate	Significant papillae/follicles less than 1 mm in diameter, and/or marked conjunctival			
	injection			
	Staining of the top of one papilla			
4 = Severe	Localized or generalized papillae/follicles 1 mm or more in diameter			
	Staining of the top of more than one papilla			

# Other Findings

Record any other finding(s) and use the following scale to grade severity:

0 = None	No other significant biomicroscopic findings
1 = Trace	Minimal findings
2 = Mild	Mild findings
3 = Moderate	Significant findings
4 = Severe	Severe findings

Note: If there are multiple other findings, on the eCRF for "Other" record the grade of the most severe in the "Result" field and record all findings (along with their individual grades) in the "If Other, Specify" field.

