#### **6.3.3.** Biomicroscopy Findings

Slit lamp biomicroscopy assessments will be performed using the ISO11980 grading at the Screening/Baseline visit (Day 1) and at Visit 3 (and at unscheduled and early exit visits, as necessary).

Biomicroscopy parameters will be summarized [eye-level summary]as a categorical variable by analysis visit:

- Limbal Hyperemia: None, Trace, Mild, Moderate, and Severe
- Bulbar Hyperemia: None, Trace, Mild, Moderate, and Severe
- Corneal Epithelial Edema: None, Trace, Mild, Moderate, and Severe
- Corneal Staining: Absent and Present
  - o Central: None, Trace, Mild, Moderate, and Severe
  - o Superior: None, Trace, Mild, Moderate, and Severe
  - o Nasal: None, Trace, Mild, Moderate, and Severe
  - o Inferior: None, Trace, Mild, Moderate, and Severe
  - Temporal: None, Trace, Mild, Moderate, and Severe
- Conjunctival Staining: None, Trace, Mild, Moderate, and Severe
- Palpebral Conjunctival Observations: None, Trace, Mild, Moderate, and Severe
- Other Findings: None, Trace, Mild, Moderate, and Severe

Shift tables will be generated using the ISO 11980 grading categories. The number and percentage of eyes shifting from categories between Baseline and Visit 3 will be summarized.

A supportive listing for biomicroscopy assessments will be provided.

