## 13. Tables, Listings, and Figures

A separate document contains the shells to be employed in this study.

- Table 14.1.1.1: Subject Disposition
- Table 14.1.1.1.2: Subject Disposition by Site
- Table 14.1.2.1.1: Major Protocol Deviations FAS
- Table 14.1.3.1.1: Summary of Demographics and Baseline Clinical Characteristics FAS
- Table 14.1.3.1.2: Summary of Demographics and Baseline Clinical Characteristics by Site FAS
- Table 14.1.4.1: Summary of Treatment Duration and Missed Doses FAS
- Table 14.2.1.1.1: Summary of IDEEL-SB Score by Analysis Visit FAS
- Table 14.2.1.1.1.2: Summary of IDEEL-SB Score by Analysis Visit PP

- Table 14.3.1.1: Overall Summary of Non-Ocular Treatment-Emergent Adverse Events (TEAEs) FAS
- Table 14.3.1.2.1: Summary of Non-Ocular Treatment-Emergent Adverse Events (TEAEs) by MedDRA PT- FAS
- Table 14.3.1.2.2: Summary of Serious Non-Ocular Treatment-Emergent Adverse Events (TEAEs) by MedDRA PT FAS
- Table 14.3.1.2.3: Summary of Non-Ocular Treatment-Emergent Adverse Events (TEAEs) Related with Study Device by MedDRA PT FAS
- Table 14.3.1.3: Overall Summary of Ocular Treatment-Emergent Adverse Events (TEAEs) FAS
- Table 14.3.1.4.1: Summary of Ocular Treatment-Emergent Adverse Events (TEAEs) by MedDRA PT FAS
- Table 14.3.1.4.2: Summary of Serious Ocular Treatment-Emergent Adverse Events (TEAEs) by MedDRA PT FAS
- Table 14.3.1.4.3: Summary of Ocular Treatment-Emergent Adverse Events (TEAEs) Related with Study Device by MedDRA PT FAS
- Table 14.3.2.1: Summary of BCVA Score (logMAR) by Analysis Visit FAS
- Table 14.3.3.1: Summary of Biomicroscopy Findings by Analysis Visit FAS

- Table 14.3.3.2: Shift from Baseline to Visit 3 Biomicroscopy Findings FAS
- Table 14.3.3.3: Summary of Corneal Staining by Analysis Visit FAS
- Table 14.3.3.4: Shift from Baseline to Visit 3 Corneal Staining FAS
- Table 14.3.4.1: Summary of Device Deficiencies FAS
- Listing 16.2.1.1: Listing of Subject Disposition
- Listing 16.2.1.2: Listing of Missed Visits FAS
- Listing 16.2.2.1: Listing of Protocol Deviations FAS
- Listing 16.2.3.1: Listing of Demographics and Baseline Clinical Characteristics FAS
- Listing 16.2.3.2: Listing of Medical History and Concomitant Medication FAS
- Listing 16.2.4.1: Listing of Missed Doses FAS
- Listing 16.2.4.1: Listing of IDEEL-SB Questionnaire FAS
- Listing 16.2.5.1: Listing of Treatment-Emergent Adverse Events (TEAEs) FAS
- Listing 16.2.6.1.1: Listing of BCVA Assessments FAS

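### The pooled worst-grade row for Other Findings can hide a new finding in an eye that already had one; a count by type, from data already collected, would show it

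*Protocol*

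**What the plan says.** **Routing.** Protocol 7.3.4.2, under the standard corneal staining assessment, says "Recurrent erosion and corneal ulceration should be recorded under" Other findings, and also "Inferior arcuate staining should be recorded under" that heading. The Other Findings subsection covers whatever else is seen: "Record any other finding(s) and use the following scale to grade severity", on a scale of 0 to 4.

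**Recording.** If an eye has more than one such finding, the site is to "record the grade of the most severe in the" Result field of the eCRF, and to "record all findings (along with their individual grades) in the" specify field (If Other, Specify).

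**Analysis.** SAP 6.3.3 lists the parameter at eye level as "Other Findings: None, Trace, Mild, Moderate, and Severe". It then says of shifts: "The number and percentage of eyes shifting from categories between Baseline and Visit 3 will be summarized". The output in SAP section 13 is "Table 14.3.3.2: Shift from Baseline to Visit 3 Biomicroscopy Findings FAS". The SAP does not plan to code or tabulate the specify text, or to count eyes with an Other finding that was absent at Baseline.

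**Corneal staining.** The same SAP section summarises corneal staining as absent or present and by five regions, one of them inferior. Neither document says whether inferior arcuate staining entered under Other Findings is also graded as corneal staining.

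**The concern.** Biomicroscopy, including corneal staining, is a listed safety endpoint (Protocol 6.3.3, SAP 6.1). The study has a single arm, so change from Baseline is the only internal reference for whether the eye surface got worse on the drops. A shift table does that job when both ends of the shift describe the same thing. Here the two ends may describe different findings: the Baseline grade can belong to an old, unrelated condition and the Visit 3 grade to the worst of that condition and something new. The row would then show stability, or even improvement, in an eye that had acquired a new finding.

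**Working it through.** No sample size or error rate is involved. The check takes the recording rule and works through what the shift row can show.

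**Set-up.** In one eye, let *b* (1 to 4) be the Baseline grade of an existing Other finding, *o* (0 to 4) its grade at Visit 3, and *n* (1 to 4) the Visit 3 grade of a new, unrelated Other finding. The recording rule gives:

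- tabulated Baseline grade = *b*
- tabulated Visit 3 grade = max(*o*, *n*)
- the row shows no shift if max(*o*, *n*) = *b*, improvement if it is below *b*, and worsening if it is above *b*.

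**Enumeration with the new finding no worse than the Baseline grade (*n* ≤ *b*):**

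| Old finding at Visit 3 | Combinations | No shift | Improvement | Worsening |
|---|---|---|---|---|
| Unchanged (*o* = *b*) | 1+2+3+4 = 10 | 10 | 0 | 0 |
| Resolved (*o* = 0) | 10 | 4 (*n* = *b*) | 6 (*n* < *b*) | 0 |
| Unchanged or better (*o* ≤ *b*) | 2+6+12+20 = 40 | 20 | 20 | 0 |
| Any grade | 50 | 20 | 20 | 10 |

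The 10 worsenings in the last line are the combinations with *o* > *b* (3+4+3+0 = 10). The old finding causes them, not the new one.

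**Two examples.**

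- Grade 2 finding at Baseline, still grade 2 at Visit 3, plus a new grade 2 inferior arcuate stain: max(2, 2) = 2, so the row reads Mild to Mild.
- Grade 3 finding at Baseline that resolves, plus a new grade 1 finding: max(0, 1) = 1, so the row reads Moderate to Trace, an improvement.

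These are counts of possible grade combinations, not expected frequencies. The effect needs a graded Other finding at Baseline and a new one in the same eye. Neither document says how often that occurs.

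**Amount of text to categorise.** 68 subjects × 2 eyes = 136 eyes, each at two scheduled visits (Day 1 and Visit 3).

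**The case against.** **The serious events are counted elsewhere.** This is the strongest objection, and it largely stands. Protocol 9.1 and the glossary define an adverse event broadly enough to take in a new corneal ulcer or erosion, and a potentially sight-threatening event meets the seriousness criteria. SAP 6.3.1 counts ocular treatment-emergent events by preferred term and by eye, with separate tables for serious and device-related events. A reader might infer that new ulcers would go uncounted in the safety report. The documents do not support that. What the adverse event route may miss is the milder finding: under Protocol 9.2, a changed study parameter is reported only if the investigator judges it clinically relevant.

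**The row is coarse, not false.** This also stands. A worst-grade row correctly reports the worst grade, every individual grade is kept in the specify field, a biomicroscopy listing is planned, and no hypothesis turns on this row. But a listing gives no numerator or percentage, and the SAP does not say that the specify text will appear in it.

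**The layout is unseen.** The table shells are in a separate document. That the Result field feeds the SAP variable, and that Other Findings is in the shift table, are inferences from SAP 6.3.3: it is listed there with the other graded parameters, just above the shift-table paragraph.

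**Corneal staining.** A reader might infer that an eye whose only staining is inferior arcuate must be tabulated as absent. The protocol does not say that. It directs an entry under Other Findings and is silent on the corneal staining grade, so recording in both places is an equally natural reading.

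**Size.** It is tempting to estimate how many subjects start with a nonzero Other grade by assuming that lid-margin findings in the evaporative and mixed groups are recorded there. Neither document mentions such findings or their frequency, so no estimate is offered.

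**Conclusion.** The point holds as a cheap improvement to the planned summaries; data capture is sound. In an eye with a graded Other finding at Baseline, a new unrelated finding of equal or lower grade never produces a worsening in the pooled row by itself (0 of 40 combinations when the old finding is unchanged or better), and in 20 of those 40 the row shows an improvement. The practical gap is mainly milder findings that are not reported as adverse events, with inferior arcuate staining the clearest case; how many eyes are affected cannot be derived from the documents. The conclusion assumes that the eCRF Result field is the source of the SAP variable and that Other Findings is included in Table 14.3.3.2. If the shells already break the findings out by type, the SAP need only say so.

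**What to change.** In SAP 6.3.3:

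- Categorise the specify-field entries by type of finding.
- Add the number and percentage of eyes and of subjects with any new or worsened Other finding against Baseline, with separate rows for recurrent erosion, corneal ulceration and inferior arcuate staining.
- Footnote any pooled Other Findings shift row as the worst grade across different findings.
- State that an eye with inferior arcuate staining counts as present in the absent/present corneal staining summary, since the protocol leaves this open.

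The cost is SAP wording, one extra table, and manual categorisation of free text for at most about 136 eyes at two scheduled visits. No new data are needed, because the individual findings and grades are already to be recorded.

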#### 7.3.4.3 BCVA

BCVA will be assessed per standard practice at the Screening/Baseline visit (D1) and at Visit 3 (and at unscheduled and early exit visits, as necessary).

#### 7.3.4.4 Device Deficiencies

Device deficiencies will be collected at the time points specified in Table 4.

# 7.4 Follow-Up Procedures and Therapy Transitions

In this study, there are no specific follow-up procedures or therapy transitions required. Following study completion, subjects will return to their previous care provider.

Alcon products associated with device deficiencies and/or product-related AEs should be returned when possible. Product returns must include the complaint number, which will be provided by study Sponsor after the case is entered in the study Sponsor's Global Product Complaint Management System (GPCMS).

Return any recoverable Alcon Product associated with a product-related AE (adverse device effect [ADE], serious adverse device effect [SADE]) or device deficiency to the Sponsor. Include the SAE/ADE or device deficiency eCRF in the return package. Maintain a copy of shipment tracking information and all documents submitted with the product.

## 7.5 Study Timetable / Schedule of Study Assessments

The schedule of study assessments is provided in Table 4.

**Table 4.** Schedule of Study Assessments

Procedure/ Assessment	Visit 1 Screening + Baseline (Day 1)	Visit 2 (phone) 15-day Follow-up (±2 days)	Visit 3 30-day / Exit (±2 days)	Unscheduled Visit / Early Exit
Informed consent	X			
Demographics	X			
Targeted medical history	X			
Targeted concomitant medications	X			
IDEEL-SB questionnaire	X		X	(X)
Inclusion/Exclusion	X			
Changes in concomitant medications		X	X	X
BCVA	X		X	(X)
Biomicroscopy (include corneal staining)	X		$\overline{X}$	(X)
AEs	X	X	X	X
Device deficiencies	X	X	X	X
Exit form	(X)		X	X
Telephone follow-up for compliance check		X		

AE: adverse event; BCVA: best corrected visual acuity;

; IDEEL-SB: Impact of Dry Eye on

Everyday Life - Symptom Bother

X) assessment performed as necessary

<sup>a On Day 1: before Systane Complete PF first dose, immediately after first dose, and 8 hours after first dose (prior to administering evening dose of Systane Complete PF)

#### 7.6 Deviations from the Clinical Protocol

When a deviation from the protocol is necessary for an individual subject, the Investigator must contact the Sponsor (or its acting representative) prior to the deviation (unless the deviation is safety related). The subject may continue in the study by mutual agreement of the Sponsor and the Investigator. A description of the deviation from the protocol and justification must be recorded on the Protocol Deviation Form.

Deviations occurring without prior approval must be assessed by the Investigator and reviewed by the Sponsor. Subject continuation must be indicated on the Protocol Deviation Form. A description of the deviation from the protocol and justification must be recorded on the Protocol Deviation Form. Unintended deviations from the protocol must be recorded on a Protocol Deviation Form within 24 hours of the identification of the deviation. The Sponsor, or Sponsor's representative must be notified.

# 7.7 Clinical Study Termination

The study Sponsor reserves the right to suspend or close the investigational site or suspend or terminate the study in its entirety at any time.

The Investigator may initiate study-site closure at any time, provided there is reasonable cause and sufficient notice is given in advance of the intended termination.

Reasons for the early closure of a study site by the Sponsor or Investigator may include but are not limited to:

- For study termination:
  - o Discontinuation of further study treatment development
- For site termination:
  - o Failure of the Investigator to comply with the protocol, the requirements of the IRB/IEC or local health authorities, the Sponsor's procedures, or Good Clinical Practice (GCP) guidelines
  - O Inadequate or no recruitment (evaluated after a reasonable amount of time) of subjects by the Investigator
  - o Total number of subjects included earlier than expected

If the clinical study is prematurely terminated or suspended by the study Sponsor:

- The study Sponsor (or its acting representative) shall:
  - Immediately notify the Investigator(s) and subsequently provide instructions for study termination.

- o Inform the Investigator and the regulatory authorities of the termination/suspension and the reason(s) for the termination/suspension.
- The Investigator shall:
  - o Promptly notify the IRB/IEC of the termination or suspension and of the reasons.
  - o Provide subjects with recommendations for poststudy treatment options as needed.

# 7.8 Subject Compensation

Where permitted by the IRB/IEC, study subjects will be compensated for participation.

#### 8 DATA COLLECTION AND ANALYSIS

#### 8.1 Subject Populations for Analysis

Two analysis data sets will be defined:

- The Full Analysis Set (FAS) will include all subjects/eyes exposed to at least one dose of Systane Complete PF. The Full Analysis Set will serve as the primary analysis set for all effectiveness and safety analyses.
- The Per Protocol (PP) population is a subset of the FAS and will exclude subjects with major protocol deviations. The PP population will be a supportive set for effectiveness analyses, as necessary.

#### **8.2** Statistical Methods

This section is a summary of the planned statistical analyses. A Statistical Analysis Plan will be finalized prior to database lock and will include a more technical and detailed description of the statistical analyses described in this section.

Statistical analyses will be presented overall and by DED groups (aqueous deficient dry eye, evaporative dry eye, mixed dry eye).

There is no statistical hypothesis for the endpoints in this study. Appropriate descriptive statistics will be computed and presented for all categorical and continuous endpoints.

- For categorical variables, the number and percentage of subjects/eyes within each category of interest will be presented.
- For continuous variables, the number of subjects/eyes with non-missing data, mean, standard deviation, range, median, minimum, and maximum will be presented.
- There will be no imputation for missing data.

All visual acuity results will be presented in logarithm of the minimum angle of resolution (logMAR) scale after applying appropriate transformations/conversions.

